9 STATISTICAL CONSIDERATIONS

Part A, dose escalation with an every 21-day dosing regimen, of the study consists of an accelerated titration design, followed by a 3+3 design, and ending in a cohort using the mTPI-2 design. During dose escalation (3+3 design), the exact sample size will be determined by the observed safety profile, which will determine the number of subjects per cohort and the number of cohorts.

Once the MTD is defined or the highest dose is tested (ie, 10 mg/kg, AIBW), up to 38 subjects can be enrolled at the MTD to refine dose selection using mTPI-2, a rule-based design similar to the 3+3 design that allows dose escalation/de-escalation. In November 2019, the selection of 7 mg/kg as the MTD/RP2D was made based on factors including safety, efficacy, and PK/PD, by the Sponsor with input from the SRC.

Part B, with an every 21-day dosing regimen, is designed to provide a preliminary assessment of efficacy at the MTD/RP2D. Given the confirmed ORR seen to date in subjects with HR-positive/HER2-negative BC receiving monotherapy CX-2009 on the every 21-day schedule, a 2-stage enrollment design will no longer be incorporated. The SRC will continue to review on-going safety and efficacy data throughout the course of the clinical study. The sample size was selected to estimate the ORR. With 40 subjects treated, if 8 subjects have confirmed objective responses, the observed ORR will be 20% (90% CI: 10% - 33%); the lower bound of the 90% CI would therefore exclude an ORR of 10%.

Part C1, dose escalation/de-escalation using the mTPI-2 design with an every 14-day dosing regimen, will enroll up to 24 subjects (3 to 6 subjects at each dose level) for the purposes of MTD/RP2D decisions.

Part C2, with an every 14-day dosing regimen, is designed to provide a preliminary assessment of clinical activity at the MTD/RP2D. Once the MTD/RP2D is defined in Part C1, expansion cohorts of up to 40 subjects in selected tumor types will be enrolled as described in Part B to evaluate the antitumor activity using the MTD/RP2D in Part C2. A 2-stage design may be incorporated into this cohort.

Part D1, dose escalation/de-escalation using the mTPI-2 design for CX-2009 with an every 14-day dosing regimen in combination with CX-072, will enroll up to 24 subjects (3 to 6 subjects at each dose level) for the purposes of MTD/RP2D decisions.

Part D2, dose expansion of CX-2009 plus CX-072 with an every 14-day dosing regimen, is designed to provide a preliminary assessment of clinical activity at the MTD/RP2D. Once the MTD/RP2D is defined in Part D1, expansion cohorts of 40 subjects in selected tumor types will be enrolled as described in Part B to evaluate the antitumor activity of CX-2009 plus CX-072. A 2-stage design may be incorporated into this cohort.

Part E1, dose escalation using the mTPI-2 design for CX-2009 with an every 21-day dosing regimen in combination with CX-072, will enroll up to 24 subjects (3 to 6 subjects at each dose level) for the purposes of MTD/RP2D decisions.

Part E2, dose expansion of CX-2009 plus CX-072 with an every 21-day dosing regimen, is designed to provide a preliminary assessment of clinical activity at the MTD/RP2D. Once the MTD/RP2D is defined in Part E1, expansion cohorts of 40 subjects in selected tumor types will be enrolled as described in Part B to evaluate the antitumor activity of CX-2009 plus CX-072. A 2-stage design may be incorporated into this cohort.

Enrollment within the expansions will be suspended if either of the following Safety Stopping Rules are met in the first 6 subjects enrolled in Parts B, C2, D2, and E2:

- DLT rate is >30% within 21 days (Parts B and E2) or within 28 days (Parts C2 and D2) of the first dose of study drug
- >20% of subjects have a treatment interruption or discontinuation within the first 6 weeks of the first dose of study drug or within 6 weeks of a single dose reduction step for subjects who experience events with their first dose of study drug

One of the major exploratory objectives aims at evaluating the relative Probody therapeutic activation in the tumor versus blood across various indications. The relative degree of Probody therapeutic activation in the tumor versus blood is expected to be influenced by Probody therapeutic dose, protease activity, and tumor target (CD166) expression. The variable nature of the protease activity and target expression in the tumor between subjects is expected to lead to variation in relative Probody therapeutic activation. For Part A2, tumor biopsies are required 3 to 5 days after the first dose of CX-2009. For the dose expansion (Part B), consent to pretreatment and on-treatment tumor biopsies will be mandatory for at least 7 subjects for each tumor type.

Based on nonclinical data, the differential activation between tumor and blood has a mean of about 20.0% and a standard deviation of about 5.0%. For Part A2 with 6 subjects enrolled in a dose cohort, the 90.0% CI (based on t-distribution with 5 degrees of freedom) for the differential activation is (16.0%, 24.0%). For each of the expansion cohorts in Parts B and C2, the 90.0% CI (based on t-distribution with 6 degrees of freedom) for the differential activation based on the best case scenario of 7 subjects is (16.3%, 23.7%), and based on the more likely scenario of 4 subjects is (14.1%, 25.9%). In addition, the variability in protease activity between subjects might further reduce our ability to measure Probody therapeutic activation in the tumor. It is anticipated that the requested tumor biopsies will provide reasonable estimates for this FIH study. If tumor biopsies are not mandatory, fewer subjects would be available for analysis, and the estimates would be less precise.

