9.1 Populations

For assessment of MTD/RP2D, the population will be based on subjects who are evaluable for DLT determination (a “DLT-evaluable” subject is defined as having received at least 1 dose of CX-2009 (or CX-2009 and CX-072) and completed the full DLT observation period (either 21 or 28 days depending on the schedule) or a subject who has withdrawn from the study drug due to a drug-related toxicity. Subjects who are not DLT evaluable may be replaced in the cohort.

For assessment of efficacy (Parts B, C2, D2 and E2), subjects must have undergone at least 1 on-study imaging assessment. Subjects who die prior to his/her first on-study scan will not be counted as evaluable for this assessment.

The efficacy evaluable group for Parts D2 and E2 will include only those subjects who are determined to be PD-L1 positive.

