9.2 Other Statistical Analyses

Statistical assessments/methods for safety, efficacy, PK/PD, and immunogenicity are found in Section 11 of the Core. In instances where the statistical analysis plan (SAP) might contradict the analyses specified in the Core, the SAP supersedes the Core.

Available data from Part A2 will be pooled with data from Part A by dose. In addition, efficacy data from Part A2 may be analyzed separately. The relationship between dose and safety/efficacy may be explored. Analyses by dose may be conducted for, but not limited to, the following endpoints: frequency of AEs of special interest, ORR, and percent reduction in tumor burden by dose. A generalized linear model may be used to adjust for covariates or to model the relationship. Because of the limited number of subjects, the above analyses will be conducted if data warrant.

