11. STATISTICAL PLAN AND ANALYSIS

Analyses common to the modules are described in the Common Core Document. Analyses specific to a Protocol Module will be described in a module-specific statistical analysis plan (SAP).

Descriptive summaries will be provided. For continuous measures, these include mean, median, standard deviation, and range. For categorical measures, these include counts and percentages.

The safety analysis population includes all enrolled subjects who receive at least one dose of study drug. The safety analysis population is used for evaluating subject characteristics, treatment administration, safety endpoints, and efficacy analyses related to PFS and OS.

The response evaluable population includes all subjects in the safety analysis population who have an adequate baseline disease assessment. The response-evaluable population is used for efficacy analyses related to objective response, including objective response rate (ORR), TTR, and DOR.

Analyses may be presented by cancer type, treatment regimen, and dose, when applicable.

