11.3.1. Efficacy Analysis Methods

The primary efficacy endpoint is the ORR and the primary efficacy analysis is based on the response-evaluable population. Exact 2-sided 95% confidence intervals will be calculated for all proportion estimates. Estimates of time-to-event endpoints (DOR, PFS, and OS) will be obtained using the Kaplan-Meier method. DOR and TTR will also be summarized using descriptive statistics for confirmed objective responders

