9.2 Response Evaluable Population (REP)

The response evaluable population includes all subjects in the safety analysis population who have an adequate baseline disease assessment and at least one post-baseline disease assessment. The response-evaluable population is used for efficacy analyses related to objective response, including objective response rate (ORR), TTR, and DOR.

10. General Statistical Considerations

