13.1.1 Primary Efficacy Endpoint

The ORR is the primary efficacy endpoint. For solid tumors, response evaluation will be based on the RECIST criteria (v1.1) and ORR is defined as the proportion of subjects with complete response (CR) or partial response (PR) on two consecutive tumor assessments with scan dates at least 4 weeks apart according to RECIST (RECIST v1.1).

The primary efficacy analysis will be based on the REP. Exact 2-sided 95% Cis (using the Clopper-Pearson method) will be calculated for all proportion estimates.

A listing of tumor data including total tumor burden, RECIST v1.1 response assessments (target lesion evaluation, non-target lesion evaluation, and overall subject response) will be provided.

Response Assessment and Best Overall Response – RECIST v1.1

Efficacy outcomes will be summarized by dose level and by cancer type using RECIST v1.1 among the REP. The overall number of subjects for each dose; and the number, proportion, and 95% exact 2-sided CI (using the Clopper-Pearson method) of confirmed CR and PR, unconfirmed CR and PR, SD, PD, not evaluable (NE), overall response (CR + PR), disease control (CR + PR + SD) will be calculated. A summary table of the above response assessments by part using RECIST v1.1 among the REP will be provided. A swim lane plot of response assessment status over time using RECIST v1.1 will be produced.

The best overall response is the best response recorded from the start of study treatment until the end of treatment taking into account any requirement for confirmation. If the best overall response is determined before the end of treatment (e.g., for an interim data cut), then it is the best response recorded from the start of study treatment until the date of the data cut.

When no imaging/measurement is done at all at a particular time point, the subject is not evaluable (NE) at that time point. If only a subset of lesion measurements are made at an assessment, usually the case is also considered NE at that time point, unless a convincing argument can be made that the contribution of the individual missing lesion(s) would not change the assigned time point response (as may happen in the case of an assessment of PD).

Complete or partial responses may be claimed only if the criteria for each are met at a subsequent time point as specified in the protocol (i.e., ~8 weeks later and no

earlier than 4 weeks later). In this circumstance, the best overall response can be interpreted as in Table 1.

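### Part B's 40-subject rationale excludes a 10% ORR on a 90% interval, but the planned ORR interval is exact 95%, on which 8/40 does not exclude 10%

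*Protocol*

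**What the plan says.** Protocol Section 9, repeated in the synopsis under Sample Size Determination, describes Part B's size in terms of precision: "The sample size was selected to estimate the ORR". The only numerical support is a hypothetical result of 8 confirmed responses among 40 treated subjects, an ORR of 20% with a 90% CI of 10% to 33%, from which it concludes that "the lower bound of the 90% CI would therefore exclude an ORR of 10"%. For Parts C2, D2 and E2 the same section refers back to Part B for how cohorts of up to 40 (C2) or of 40 (D2, E2) are to be enrolled, and adds that a 2-stage design may be used.

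For analysis methods, Protocol Section 9.2 points elsewhere: "Statistical assessments/methods for safety, efficacy, PK/PD, and immunogenicity are found in Section 11 of the Core". Core Section 11.3.1 reads: "Exact 2-sided 95% confidence intervals will be calculated for all proportion estimates". SAP Section 13.1.1 agrees and names the method: "Exact 2-sided 95% Cis (using the Clopper-Pearson method) will be calculated for all proportion estimates".

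The denominator also varies. The sample-size example counts treated subjects. Protocol Section 9.1 says that for the efficacy assessment "subjects must have undergone at least 1 on-study imaging assessment", and SAP Section 9.2 limits the response evaluable population to treated subjects "who have an adequate baseline disease assessment and at least one post-baseline disease assessment". Core Section 11 asks only for the baseline assessment: "The response evaluable population includes all subjects in the safety analysis population who have an adequate baseline disease assessment". Protocol Section 9.2 gives the SAP precedence over the Core where they conflict.

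**The concern.** The stated reason for 40 subjects is that a plausible result, 20% observed, would rule out an ORR of 10%. The interval behind that statement is not one the plan will produce. If the planned interval is wider and its lower bound falls below 10% at the same result, the study report would show 8/40 failing to do what the protocol said it would do.

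A second risk is that, with two confidence levels in the documents and neither tied to the 10% comparison, the level could be chosen after a borderline 8/40 has been seen.

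The conflict does not depend on the SAP version. The SAP was written against Module Amendment 06, but the Core is Appendix A of the reviewed protocol and the Module itself directs the reader to it for efficacy methods.

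**Working it through.** **Inputs.** n = 40, x = 8, reference ORR 10%, 90% level (Protocol Section 9). Exact two-sided 95% (Core 11.3.1), Clopper-Pearson (SAP 13.1.1).

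**Formula.** For x responders in n at two-sided level 1 − α:

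- lower bound = α/2 quantile of Beta(x, n − x + 1)
- upper bound = 1 − α/2 quantile of Beta(x + 1, n − x)

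The lower bound exceeds 10% exactly when P(X ≥ x | n, 0.10) < α/2.

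**Step 1: reproduce the protocol's figure (90%, α/2 = 0.05).** For 8/40, Beta(8, 33) at 0.05 gives 10.36% and Beta(9, 32) at 0.95 gives 33.20%. These round to the stated 10% and 33%. P(X ≥ 8 | 40, 0.10) = 0.0419 < 0.05, so 10% is excluded, narrowly. For 7/40 the lower bound is 8.51%, so 8 is the minimum at 90%.

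**Step 2: the planned interval (95%, α/2 = 0.025).**

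| Result | ORR | Exact 95% CI | P(X ≥ x given 10%) | Excludes 10%? |
|---|---|---|---|---|
| 8/40 | 20.0% | 9.05% to 35.65% | 0.0419 | no |
| 9/40 | 22.5% | 10.84% to 38.45% | 0.0155 | yes |

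The lower bound for 8/40 moves from 10.36% to 9.05%, a drop of 10.36 − 9.05 = 1.31 percentage points, and the minimum count rises from 8 to 9. If the true ORR were 20% (the example's observed value, taken here as an assumption), the chance of a lower bound above 10% would fall from P(X ≥ 8) = 56.3% to P(X ≥ 9) = 40.7%.

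**Step 3: fewer than 40 evaluable.** With 8 responders held fixed:

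| Evaluable | 90% lower | 95% lower | Minimum responders, 90% | Minimum responders, 95% |
|---|---|---|---|---|
| 40 | 10.36% | 9.05% | 8 | 9 |
| 39 | 10.64% | 9.30% | 8 | 9 |
| 38 | 10.93% | 9.55% | 8 | 9 |
| 37 | 11.24% | 9.83% | 8 | 9 |
| 36 | 11.57% | 10.12% | 8 | 8 |
| 35 | 11.91% | 10.42% | 8 | 8 |

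The mismatch therefore affects the protocol's example at 37 to 40 evaluable and disappears for 8 responders at 36 or fewer.

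**Step 4: dependence on method.** A 95% Wilson interval for 8/40 is 10.50% to 34.76% and would exclude 10%. Both documents specify exact intervals and the SAP names Clopper-Pearson, so Wilson is not the planned analysis.

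**The case against.** The best counter-argument is that nothing is strictly contradicted. The protocol's example is conditional, names its 90% level openly and is correct at that level. It never says the reported interval will be 90%, and the Core's sentence does not forbid another interval. Core Section 11.7 leaves sample-size justification to the Module, so planning at one level and reporting at another can be read as a difference of purpose. Part B is a preliminary estimate with no hypothesis test, alpha, power or success rule at 10%, so no decision turns on the bound. If several subjects are not evaluable, the issue disappears for 8 responders. Enrollment has also stopped: SAP Section 4.2 lists 99 treated subjects, 3 of them in Part B, and SAP Section 8 confirms none in C2, D1 or D2.

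Most of this stands, and it limits the weight of the point. It does not remove it. The protocol goes beyond describing interval width: it claims that a named ORR would be excluded and offers this as the support for 40. The only ORR interval that the plan commits to does not have that property at 8/40. Loss of evaluable subjects is no defence of a sentence that assumes all 40.

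**Conclusion.** The concern holds and is minor. The 90% figure is arithmetically right, but the exclusion of 10% at 8/40 is not delivered by the planned exact 95% interval, under which 9/40 is needed. The size is about 1.3 percentage points at the lower bound, or one responder.

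This rests on Clopper-Pearson limits, as the SAP specifies, and on 37 to 40 of the 40 treated subjects being response-evaluable. No decision rule is broken and no result under this SAP changes, because Part B closed with 3 subjects. The sentence matters only if the text is reused for an expansion cohort that takes its size rationale from Part B.

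**What to change.** Make one of two changes.

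- **(a) Keep the 90% rationale and plan for it.** State that an exact 90% Clopper-Pearson interval for expansion-cohort ORR is the one compared with 10%, reported alongside the 95% interval. With 8 responders its lower bound exceeds 10% at 40 evaluable and at any smaller number.
- **(b) Restate the example on the planned interval**, in Protocol Section 9 and the synopsis. Suggested wording: if all 40 treated subjects are response-evaluable, 8 confirmed responses give an ORR of 20% (exact 95% CI 9.1% to 35.6%), and 9 (22.5%, 10.8% to 38.5%) are needed for the lower bound to exceed 10%.

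Either costs a sentence and needs no extra subjects, data or design change. The downside of (a) is one more interval to report. The downside of (b) is a slightly less favourable stated figure.

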9.1 Populations

For assessment of MTD/RP2D, the population will be based on subjects who are evaluable for DLT determination (a “DLT-evaluable” subject is defined as having received at least 1 dose of CX-2009 (or CX-2009 and CX-072) and completed the full DLT observation period (either 21 or 28 days depending on the schedule) or a subject who has withdrawn from the study drug due to a drug-related toxicity. Subjects who are not DLT evaluable may be replaced in the cohort.

For assessment of efficacy (Parts B, C2, D2 and E2), subjects must have undergone at least 1 on-study imaging assessment. Subjects who die prior to his/her first on-study scan will not be counted as evaluable for this assessment.

The efficacy evaluable group for Parts D2 and E2 will include only those subjects who are determined to be PD-L1 positive.

